2 Schedule of Activities	Removal of injection site inspection assessment.	GM-CSF dose now being given as an IV infusion and no longer as an injection and therefore not required.
2 Schedule of Activities	Clarification of footnote for flow cytometry sample time-points and addition of a 9hour 40 minutes (10 hours post end of GM-CSF infusion) time-point for the GM-CSF group only.	Given the change of administration of GM-CSF (LEUKINE) from subcutaneous to IV infusion over 2 hours the minus 30 minutes pre-blister induction was no longer valid and so was changed to say pre challenge agent. The minus 5 minute time-point was clarified to mean pre-blister induction. The 9hour 40minutes post blister induction time- point was added as it is anticipated that the peak leukocyte count will occur between 8-12 hours and this will be required to make an accurate decision at dose escalation.
2 Schedule of Activities	Session 2 Day 2 urine collection time-point removed and footnote 12 moved to Day 1.	This was an error in the previous protocol as the urine collection was only until 12 hours post challenge agent.
4 Objectives and Endpoints	Clarification to primary objective to remove the wording "in cantharidin-induced skin blisters"	To clarify that the primary objective was based on blood and urine samples.
5 Study Design	Change of dose for GM-CSF in the study design schematic.	Given the change of administration of GM-CSF (LEUKINE) from subcutaneous to IV infusion the minimum and

Section # and Name	Description of Change	Brief Rationale
		maximum doses needed to change, as mentioned above.
5.1 Overall Design	Study design schematic session 2 changed to include pre- challenge blood draw instead of minus 30 minutes and 09:40 blood draw time-point added for GM-CSF only.	Given the change of administration of GM-CSF (LEUKINE) from subcutaneous to IV infusion over 2 hours the minus 30 minutes pre-blister induction was no longer valid.
5.5.3 GM-CSF (Dose Justification)	Initial dose amended and maximum dose amended. Removed the increments of 5µg/kg.	Initial dose amended to reflect change of GM-CSF administration from subcutaneous to IV infusion dose and to remain consistent with clinical practice in dosing GM-CSF therapeutically the dose will be calculated by body surface area. Increments of 5 µg/kg was now far too high with the change from subcutaneous injection to IV infusion and so the increments was removed.

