2. SCHEDULE OF ACTIVITIES (SOA)

Any changes in the timing or addition of time points for any planned study assessments must be documented and approved by the relevant study team member and then archived in the sponsor and site study files, but will not constitute a protocol amendment. The IRB/IEC will be informed of any safety issues that require alteration of the safety monitoring scheme or amendment of the ICF.

2016N309726_01

CONFIDENTIAL

207654

PROCEDURE	Screening	SI	ESSION	1	Interim inspectio n		SESS	ION 2		1st follow-up	2nd follow-up		
Day:	Within 30 days of Day 1	Day 1	Day 2	Day 3	Minimum 2 wks (max 4 weeks) after end of session 1	Day -1	Day 1	Day 2	Day 3	Minimum 2 wks (max. 4 weeks) after end of session 2	Approx. 5wks after end of session 2		
Attend Unit	Х	Х	Х	Х	Х	X3	Х3	Х	Х	Х	Х	1.	Brief physical exam only
Informed Consent	Х											2.	Within an hour before
Inclusion/Exclusion checklist	Х					Х							cantharidin application
Medical /medication history	Х											3.	Overnight stay in the unit
Demographics	Х											4.	Additional clinical lab
Body weight	Х					Х							assessments may be
Drug/alcohol test	Х	Х				Х						_	performed, if necessary
Physical Exam	Х	X1				Х	X ¹			X1		5. 6.	Before blister fluid sampling After the last blister fluid
Vital Signs and temperature	Х	X2				Х	X8	Х		Х	Х	0.	sampling at each session
ECG	Х					Х	Х					7.	Multiple blood draws at the
Telemetry							Х						following time points: Pre
Visual forearm check (including blister healing and cosmetic assessment)	Х	X ²			Х	Х	X ²			Х	Х		challenge, , 5 mins (i.e. Pre-blister induction), 10 min, 25 min, 40
Cantharidin application (Session 2 only: 20 minutes post end of LPS or GM-CSF challenge)		Х					Х						min, 1hr:10mins, 1hr:40mins, 2hr:40mins, 5hr:40mins with respect to start of blister induction
AE assessment/Con Meds		«-									»	8.	Every half hour for the first 4
SAE	«-										»	1	hours after challenge, hourly
Clinical Chemistry, Haematology, and Urinalysis	Х	Х	Х	Х		X	Х	Х	Х				until 8 hours and then 8 hourly until discharge. Frequency can be increased if symptomatic
Mediators blood sample		X2	X5	X5			X7	X5	X5			9.	For flow cytometry and
Flow cytometry blood sample		X2	X5	X5			Х9	X5	X5				transcriptomic blood samples:
For LPS only: Ex vivo							X ¹⁰						Multiple blood draws at the

2016N309726_01

CONFIDENTIAL

207654

PROCEDURE	Screening	SE	SSION	1	Interim inspectio n		SESS	ION 2		1st follow-up	2nd follow-up		

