Risk of Respiratory Symptoms	Sequestration of granulocytes in the pulmonary circulation has been documented following LEUKINE infusion12 and dyspnoea has been reported occasionally in patients treated with LEUKINE. Special attention should be given to respiratory symptoms during or immediately following LEUKINE infusion, especially in patients with pre-existing lung disease. In patients displaying dyspnoea during LEUKINE administration, the rate of infusion should be reduced by half. If respiratory symptoms worsen despite infusion rate reduction, the infusion should be discontinued. Subsequent IV infusions may be administered following the standard dose schedule with careful monitoring. LEUKINE should be administered with caution in patients with hypoxia.	Patients with known respiratory disease will be excluded from the study (as described in the Exclusion criteria), as well as patients with current or recent (<30 days) infection.
Risk of cardiovascular Symptoms	Occasional transient supraventricular arrhythmia has been reported in uncontrolled studies during LEUKINE administration, particularly in patients with a previous history of cardiac arrhythmia. However, these arrhythmias have been reversible after discontinuation of LEUKINE.	Patients with pre-existing cardiac disease will not be eligible to participate. In addition, we will use telemetry for a minimum of 6 hours following dosing, or until normal for 4 hours (whichever is longer).

2016N309726_01

CONFIDENTIAL

Potential Risk of Clinical Significance	Summary of Data/Rationale for Risk	Mitigation Strategy
	LEUKINE should be used with caution in patients with pre-existing cardiac disease.	

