### 5.2. Baseline Definitions

For all endpoints (except as noted in baseline definitions) the baseline value will be the latest pre-dose assessment with a non-missing value, including those from unscheduled visits. If time is not collected, Day 1 assessments are assumed to be taken prior to first dose of challenge and used as baseline.

Parameter	Study Assessments Considered as Baseline				Baseline Used in Data Display
	Screening	Session 1 Day 1	Session 1 Day 2	Session 2 Day 1	
Biomarkers					
LPS: TNF- $\alpha$ , IL6 GM-CSF: WBC (Total leukocyte counts)		X	X	X	Session 2 Day 1 (Pre Blister Induction)
Blood		X			Session 1 Day 1 (Pre Blister Induction)
Blister			X		Session 1 Day 2 (24 HR)
Urine			X		Session 1 Day 2 (Pre Fluid Sampling)
In Vivo LPS or GM-CSF				X	Session 2 Day 1 (Pre Blister Induction)
Safety					
Vital Signs & Temperature	X	X			Session 1 Day 1
ECG	X				Screening
Labs	X	X			Session 1 Day 1

Unless otherwise stated, if baseline data is missing no derivation will be performed and baseline will be set to missing.

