#### 7.1.2. Summary Measure

Challenge	Endpoint
LPS	Absolute values and change from baseline in TNF- $\alpha$ , IL-6 and PGDM across the time course Baseline: 
 
• TNF-<math>\alpha</math>, IL-6: Session 2: Day 1 (Pre Blister Induction)
 
• PGDM: Session 1 Day 2 (Pre Fluid Sampling)
 

GM-CSF	Absolute values and change from baseline in total leukocyte across the time course 
 
• Baseline = Session 2: Day 1 (Pre Blister Induction)
 

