## 10. APPENDICES

### 10.1. Appendix 1: Schedule of Activities

#### 10.1.1. Protocol Defined Schedule of Events

PROCEDURE	Screening	SESSION 1			Interim inspection	SESSION 2				1st follow-up	2nd follow-up	
		Day 1	Day 2	Day 3		Day -1	Day 1	Day 2	Day 3			
Day:	Within 30 days of Day 1				Minimum 2 wks (max 4 weeks) after end of session 1					Minimum 2 wks (max. 4 weeks) after end of session 2	Approx. 5wks after end of session 2	
Attend Unit	X	X	X	X	X	X 	X 	X	X	X	X	1. Brief physical exam only
Informed Consent	X											2. Within an hour before cantharidin application
Inclusion/Exclusion checklist	X					X						3. Overnight stay in the unit
Medical /medication history	X											4. Additional clinical lab assessments may be performed, if necessary
Demographics	X											5. Before blister fluid sampling
Body weight	X					X						6. After the last blister fluid sampling at each session
Drug/alcohol test	X	X				X						7. Multiple blood draws at the following time points: Pre challenge, .
Physical Exam	X	X 				X	X 			X 		5 mins (i.e. Pre-blister induction), 10 min, 25 min, 40 min, 1hr:10mins, 1hr:40mins, 2hr:40mins, 5hr:40mins with respect to start of blister induction
Vital Signs and temperature	X	X 				X	X 	X		X	X	8. Every half hour for the first 4 hours after challenge, hourly until 8 hours and then 8 hourly until discharge. Frequency can be increased if symptomatic
ECG	X					X	X					9. For flow cytometry and transcriptomic blood samples: Multiple blood draws at the
Telemetry							X					
Visual forearm check (including blister healing and cosmetic assessment)	X	X 			X	X	X 			X	X	
Cantharidin application (Session 2 only: 20 minutes post end of LPS or GM-CSF challenge)		X					X					
AE assessment/Con Meds		«-----»										
SAE		«-----»										
Clinical Chemistry, Haematology, and Urinalysis 	X	X	X	X		X	X	X	X			
Mediators blood sample		X 	X 	X 			X 	X 	X 			
Flow cytometry blood sample		X 	X 	X 			X 	X 	X 			
For LPS only: Ex vivo							X 					

PROCEDURE	Screening	SESSION 1			Interim inspection	SESSION 2				1st follow-up	2nd follow-up	
		Day 1	Day 2	Day 3		Day -1	Day 1	Day 2	Day 3			

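### The SAP's baseline label for TNF-alpha, IL-6 and leukocytes is the name its own schedule gives to a sample drawn 15 minutes after the challenge, so the label must be reconciled

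*SAP*

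**What the plan says.** - **Baseline label.** For the LPS primary markers TNF-alpha and IL-6, SAP 7.1.2 gives the baseline as "Session 2: Day 1 (Pre Blister Induction"). For the GM-CSF primary marker, total leukocytes, it gives "Baseline = Session 2: Day 1 (Pre Blister Induction"). The table in SAP 5.2 uses the same label for all three. PGDM has a different baseline, on Session 1 Day 2.
- **Schedule.** Footnote 7 in SAP 10.1.1 (and in Protocol section 2) covers the mediator blood samples. It lists a pre-challenge draw first and then, as a separate item, "5 mins (i.e. Pre-blister induction), 10 min, 25 min, 40 min, 1hr:10mins, 1hr:40mins, 2hr:40mins, 5hr:40mins with respect to start of blister induction". The Protocol's summary of changes confirms the sign: "The minus 5 minute time-point was clarified to mean pre-blister induction".
- **Timing of induction.** Cantharidin is applied in "Session 2 only: 20 minutes post end of LPS or GM-CSF challenge".
- **Flow cytometry.** SAP 10.3.3 assigns the primary white-cell count to flow cytometry. Footnote 9 schedules flow draws on Session 2 Day 1 at pre-challenge, 40 min, 2 h 40, 5 h 40 and, for GM-CSF, 9 h 40. There is no -5 min flow draw.
- **Shell.** The mock table BIO_T1 in SAP 10.8 has PRE BLISTER INDUCTION and -5 MIN as two separate rows for Session 2 Day 1.
- **General rule.** SAP 5.2 takes the last available pre-dose value as baseline, but excepts whatever its table specifies. It adds that "if baseline data is missing no derivation will be performed and baseline will be set to missing".

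**The concern.** Within one document the same words point to two samples. A programmer who looks up the baseline label in the SAP's schedule finds a sample taken after dosing. One who looks in the mock table finds a row that comes before, and is distinct from, the -5 min sample. The general pre-dose rule does not settle the matter, because it yields to the table that carries the label.

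The value defines change from baseline for three of the four primary markers. It also feeds the Part II criteria in SAP 3.2, which compare each participant's largest increase with fixed cut-offs: 50 pg/mL for each cytokine and 5 giga/L for leukocytes. These criteria turn on at least one participant, with four planned per agent at the chosen dose, so one participant's baseline could matter.

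**Working it through.** **1. Where the named sample falls.** Inputs: induction is 20 min after the end of the challenge (Protocol section 2), and the sample is 5 min before induction (footnote 7).

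Minutes after end of challenge = minutes relative to induction + 20.

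- Named sample: -5 + 20 = 15 min. This reproduces the first post-dose draw of 15 minutes stated in Protocol 5.1.
- Check: 5 h 40 + 20 min = 6 h, the post-LPS time of the ex vivo sample in Protocol 9.7.1.3.
- Check: 9 h 40 + 20 min = 10 h after the end of the GM-CSF infusion, as in the Protocol's summary of changes.

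Measured from the start of dosing, with administration times from Protocol 7.1:

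- LPS, given over 1 to 2 min: 15 + 1 to 15 + 2 = 16 to 17 min.
- GM-CSF, given over about 2 h: 15 + 120 = 135 min, or 2 h 15 min.

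**2. What each reading selects.**

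| Marker | Label read by schedule | Label read by shell |
|---|---|---|
| TNF-alpha, IL-6 | -5 min mediator sample, 15 min post-challenge | Row before -5 MIN; the only earlier scheduled mediator draw that day is pre-challenge |
| Total leukocytes (flow) | No scheduled draw | Pre-challenge, the only scheduled flow draw before induction that day |
| PGDM | Not affected | Not affected |

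**3. What a post-dose baseline would do.** If the marker has already moved by x when the baseline is drawn, then

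recorded change = true change - x.

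The documents give no value of x. Purely as an illustration, assume x between 0 and 25 pg/mL for a cytokine. A true rise of 50 pg/mL is then recorded as 50 - 0 = 50 down to 50 - 25 = 25 pg/mL, against a cut-off of 50. At 15 minutes after LPS the movement may well be small. No corresponding calculation is given for leukocytes, because the schedule has no flow sample at that time from which such a baseline could come.

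**The case against.** The strongest reply is that the SAP already means the pre-challenge sample. The shell separates the two rows. The general rule in 5.2 is pre-dose. The 5.2 row for these markers lists Session 1 Day 1, Session 1 Day 2 and Session 2 Day 1 as candidates and takes the last, which fits a latest-pre-dose choice. The same label is used correctly for Session 1, where there is no challenge, so it may simply have been carried over. This stands as the likelier explanation. It does not remove the conflict, because the schedule in the same SAP still gives the name to a post-dose sample.

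Three stronger inferences are tempting, and the documents support none of them.

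- **The leukocyte rise is inflated.** A reader might infer this from the Protocol's risk table: "Sequestration of granulocytes in the pulmonary circulation has been documented following LEUKINE infusion". That entry gives neither size nor timing. Protocol 3.2 says that GM-CSF mobilises white cells from the marrow, so even the direction is open. Above all, no -5 min flow draw is scheduled. A haematology sample is planned that day without a clock time, but SAP 10.3.3 assigns the primary count to flow cytometry.
- **The GM-CSF change from baseline will be blank.** The rule on missing baselines covers absent data, not an ambiguous name for a sample that was collected.
- **All primary results and the Part II decision depend on the label.** PGDM has its own baseline, and the LPS rule also requires PGDM below 1.3x. The GM-CSF decision considers all biomarkers. The interim is descriptive, shows absolute values as well as changes, and lists actual sampling times. This SAP version covers only dose escalation and the interim.

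**Conclusion.** The point holds as a labelling conflict in an operative primary-endpoint definition. By the schedule, the TNF-alpha and IL-6 baseline is 15 minutes after the end of the challenge, and the flow-cytometry leukocyte baseline corresponds to no scheduled draw. By the shell, the baseline is probably the pre-challenge sample, wrongly named. A post-dose baseline is possible but not demonstrated.

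The timing rests only on figures in the documents. The size and direction of any bias cannot be derived from them, and the cytokine range in the working is an assumption that shows the mechanism only. If the dataset check finds the label on the pre-challenge samples, no numerical problem remains and only the wording needs correction. This is a clarification to make before the Part II criteria are applied, not evidence that the interim results are wrong.

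**What to change.** 1. In SAP 5.2, 7.1.2 and the shells, name the baseline for these three markers Session 2 Day 1, Pre challenge, defined as the last sample before the start of the LPS injection or GM-CSF infusion. The 5.2 row for the in vivo challenge carries the same label and should be reviewed at the same time.
2. State that the -5 min sample is a post-challenge time point and is not used as baseline.
3. State that the leukocyte baseline is the pre-challenge flow-cytometry sample.
4. Before applying the Part II increase-from-baseline criteria, check in the Part I datasets, by actual sampling time against dosing time, that the baseline label sits on the pre-challenge sample.

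The cost is a few words in the SAP, a shell label and one dataset check. No new samples or analyses are needed.

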#### 7.1.3. Population of Interest

The primary biomarker analyses will be based on the “Safety” population, unless otherwise specified.

#### 7.1.4. Strategy for Intercurrent (Post-Randomization) Events

No Strategy for Intercurrent (Post-Randomization) Events has been planned for this study.

#### 7.1.5. Statistical Analyses / Methods

Details of the planned displays are provided in [Appendix 7: List of Data Displays](#) and will be based on GSK Data Standards and statistical principles.

Unless otherwise specified, endpoints / variables defined in Section [7.1.1](#) will be summarised using descriptive statistics, graphically presented (where appropriate) and listed.

## 7.2. Secondary Biomarker Analyses

Unless otherwise stated, analyses will apply to the interim analyses.

### 7.2.1. Endpoint / Variables

There are several different types of biomarker samples collected during the study:

- Biomarkers from skin blister fluid (i.e. mediators and flow cytometry)
- Biomarkers from blood sample (i.e. mediators, flow cytometry, ex vivo stimulation (LPS only) and transcriptome)
- Biomarkers from urine (Primary endpoints)

The secondary endpoints of interest with respect to the biomarkers mentioned above:

Endpoint
Soluble and cellular inflammatory biomarkers in cantharidin-induced skin blisters at baseline versus systemic challenge with LPS or GM-CSF in healthy participants
Time course of circulating soluble and cellular inflammatory biomarker upregulation

### 7.2.2. Summary Measure

Absolute values and change from baseline of soluble and cellular inflammatory biomarkers across the time course.

Note: In the Interim Analysis, for the biomarkers from skin blister fluid, values will be averaged across arms (left and right) for each participant. These averaged values will be used in tables and figures.

If one of the values is not collected or is missing, then the single value present in the data will be used in tables and figures. Appropriate footnotes will be provided to reflect data are not an average value.

### 7.2.3. Population of Interest

The secondary biomarker analyses will be based on the “Safety” population, unless otherwise specified.

### 7.2.4. Strategy for Intercurrent (Post-Randomization) Events

No Strategy for Intercurrent (Post-Randomization) Events has been planned for this study.

### 7.2.5. Statistical Analyses / Methods

Details of the planned displays are provided in [Appendix 7: List of Data Displays](#) and will be based on GSK Data Standards and statistical principles.

Unless otherwise specified, endpoints / variables defined in Section 7.2.1 will be summarised using descriptive statistics, graphically presented (where appropriate) and listed.

### **7.3. Exploratory Biomarker Analyses**

#### **SomaLogic**

- The full panel of analytes contains 1305 proteins, and these will be measured from 88 plasma samples and 32 blister samples.
- Data will be delivered as relative fluorescence units, in two batches (one for each sample type).
- Data will be viewed as individual proteins and individual donors. This provides indication of how proteins change within an individual by reviewing the data. However, if effects across participants (i.e. N=4 for LPS or N=4 for GM-CSF) needs to be assessed, data will be normalised prior to analyses.
- Data will only be analysed at the end of the study as part of the Final Reporting. Further considerations for analysis will be detailed in the RAP as part of the Final Reporting.

#### **RNA Seq Data**

- RNAseq data will provided by Expression Analysis at Q Squared Solutions in a FASTQ file format. Data in this format will be directly analysed by GSK Computational biology groups. Analysis summary files containing summaries of information such of alignment statistics, mapping quality, base distributions, most frequent gene detected and total number of genes, by sample, will be generated. RNAseq will be analysed outside this reporting effort.

## **8. SAFETY ANALYSES**

The safety analyses will be based on the “Safety” population, unless otherwise specified. There are no Safety Analyses planned for the Interim.

## 10. APPENDICES

### 10.1. Appendix 1: Schedule of Activities

#### 10.1.1. Protocol Defined Schedule of Events

PROCEDURE	Screening	SESSION 1			Interim inspection	SESSION 2				1st follow-up	2nd follow-up	
		Day 1	Day 2	Day 3		Day -1	Day 1	Day 2	Day 3			
Day:	Within 30 days of Day 1				Minimum 2 wks (max 4 weeks) after end of session 1					Minimum 2 wks (max. 4 weeks) after end of session 2	Approx. 5wks after end of session 2	
Attend Unit	X	X	X	X	X	X 	X 	X	X	X	X	1. Brief physical exam only
Informed Consent	X											2. Within an hour before cantharidin application
Inclusion/Exclusion checklist	X					X						3. Overnight stay in the unit
Medical /medication history	X											4. Additional clinical lab assessments may be performed, if necessary
Demographics	X											5. Before blister fluid sampling
Body weight	X					X						6. After the last blister fluid sampling at each session
Drug/alcohol test	X	X				X						7. Multiple blood draws at the following time points: Pre challenge, .
Physical Exam	X	X 				X	X 			X 		5 mins (i.e. Pre-blister induction), 10 min, 25 min, 40 min, 1hr:10mins, 1hr:40mins, 2hr:40mins, 5hr:40mins with respect to start of blister induction
Vital Signs and temperature	X	X 				X	X 	X		X	X	8. Every half hour for the first 4 hours after challenge, hourly until 8 hours and then 8 hourly until discharge. Frequency can be increased if symptomatic
ECG	X					X	X					9. For flow cytometry and transcriptomic blood samples: Multiple blood draws at the
Telemetry							X					
Visual forearm check (including blister healing and cosmetic assessment)	X	X 			X	X	X 			X	X	
Cantharidin application (Session 2 only: 20 minutes post end of LPS or GM-CSF challenge)		X					X					
AE assessment/Con Meds		«-----»										
SAE		«-----»										
Clinical Chemistry, Haematology, and Urinalysis 	X	X	X	X		X	X	X	X			
Mediators blood sample		X 	X 	X 			X 	X 	X 			
Flow cytometry blood sample		X 	X 	X 			X 	X 	X 			
For LPS only: Ex vivo							X 					

PROCEDURE	Screening	SESSION 1			Interim inspection	SESSION 2				1st follow-up	2nd follow-up	
		Day 1	Day 2	Day 3		Day -1	Day 1	Day 2	Day 3			
Day:	Within 30 days of Day 1				Minimum 2 wks (max 4 weeks) after end of session 1					Minimum 2 wks (max. 4 weeks) after end of session 2	Approx. 5wks after end of session 2	
stimulation blood sample												following time points: Pre challenge, 40 mins, 2hr:40mins and 5hr:40mins (and 9hr 40mins for GM-CSF for flow cytometry only) with respect to start of blister induction
Transcriptomic blood sample							X 					10. Ex vivo stimulation blood sample: 2 samples (one null and one LPS tube) to be taken pre-dose and 2 samples (one null and one LPS tube) to be taken at 5hrs:40mins post blister induction
Urine sampling for PD			X 				X 					11. Pre-challenge urine sample will be collected in session 1. For the post-challenge samples in session 2, participants will be encouraged to pass urine immediately before LPS dosing and each urine void will be collected after LPS until 12 hours post-LPS
For LPS only: Intravenous hydration with normal Saline at a rate of 250 mL / hr							X 					12. From 4 hours prior to LPS until 8 hours after LPS
In vivo LPS or GM-CSF challenge							X 					
Blister sample for biomarkers			X	X				X	X			
Pain rating 				X					X			
Participant diary card given to participant to record blister healing		X					X					

